8.4.4 Safety Analyses

Descriptive statistics of safety will be presented using National Cancer Institute (NCI) Common Terminology Criteria for Adverse Events (CTCAE) version 4.0 by cohort. All treatment emergent AEs, drug-related AEs, SAEs and drug-related SAEs will be tabulated using worst grade per NCI CTCAE v 4.0 criteria by system organ class and preferred term.

On-study lab parameters including hematology, chemistry, liver function, thyroid function and renal function will be summarized using worst grade per NCI CTCAE v 4.0 criteria.

Safety during Induction Period: see primary endpoint definition.

Safety during Induction Period 1: events considered will be those with an onset date during Induction Period 1. Rates of treatment related AEs will be computed using subjects treated in the induction Period 1. Treatment related AEs will be tabulated using worst CTC grades by system organ class and preferred term.

- For subjects who discontinue Induction Period 1 early and enter the Follow-Up Period, AEs that occur in Follow-Up will not be included.
- For subjects who discontinue treatment before the end of Induction Period 1 but who are eligible to enter the Induction period 2, AEs that occur before end of Induction Period 1 will be included, even if they occur after dosing ends while they are waiting to enter the next study period

• AEs with an onset date after start of subsequent anti-cancer therapy, or start date of Induction Period 2 treatment will not be included.

Safety during Induction Period 2: events considered will be those with an onset date during Induction Period 2. Rates of treatment related AEs will be computed using subjects treated in the induction Period 2. Treatment related AEs will be tabulated using worst CTC grades by system organ class and preferred term.

- For subjects who discontinue Induction Period 2 early and enter the Follow-Up Period, AEs that occur in Follow-Up will not be included.
- For subjects who discontinue treatment before the end of Induction Period 2 but who are
 eligible to enter Continuation Period, AEs that occur before end of Induction Period 2
 will be included, even if they occur after dosing ends while they are waiting to enter the
 next study period
- AEs with an onset date after start of subsequent anti-cancer therapy, or start date of Continuation Period treatment will not be included. Worst CTC grades by system organ class and preferred term during Induction Period 2 will be reported.

The same analysis will be performed excluding AEs persisting from Induction Period 1 that are downgraded in Induction Period 2 compared to last grade observed in Induction Period 1.

Safety during Continuation Period: events considered will be those with an onset date during Continuation Period. Rates will be computed using subjects treated in the Continuation Period.

Overall safety on-treatment: events considered will be those with an onset date after (or on, if AE) first day of Induction Period treatment and up to 100 days after the last dose of study drug. Rates will be computed using all treated subjects.

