- Subjects who do not receive all planned doses in Induction Period 1, including those who discontinue Induction Period 1 treatment early due to progression or discontinuation criteria (Section 4.3.6.2), are to continue their scheduled study assessments (as per Table 5.1-2 and Table 5.1-3) and are still eligible to receive the alternative treatment in Induction Period 2, starting at Week 13.
- After completion of Induction Period 1, subjects will proceed to Induction Period 2, regardless of the results of the tumor assessment at the end of Induction Period 1.

3.1.2.2 Induction Period 2

- Induction Period 2 begins at Week 13 and continues to Week 25.
 - Subjects in Cohort A will receive ipilimumab at a dose of 3 mg/kg as a 90 minute IV infusion every 3 weeks (21 days) for up to 4 doses.
 - Subjects in Cohort B will receive nivolumab at a dose of 3 mg/kg as a 60 minute IV infusion every 2 weeks (14 days) for up to 6 doses.
- Subjects with drug-related AEs after the last dose in Induction Period 1 who fail to meet retreatment criteria (Section 4.3.4.2) at Week 13 will still begin Induction Period 2 at Week 13 and require omission of the initial dose(s) in Induction Period 2 until retreatment criteria are met.
- Study assessments will be conducted as outlined in Table 5.1-2 and Table 5.1-3.
- All subjects, including those who discontinue study treatment prior to receiving all planned doses during Induction Period 2, must have a tumor assessment at Week 25 (after the last dose of Induction Period 2 and prior to the first dose of the Continuation Period).
- Subjects who have clinical or radiographic progressive disease prior to the completion of Induction Period 2 are to remain on their current study treatment for the remainder of Induction Period 2, provided they are tolerating study treatment and do not have rapid clinical deterioration

• Subjects who do not receive all planned treatment doses in Induction Period 2, including those who discontinue Induction Period 2 treatment early due to progression or discontinuation criteria in Section 4.3.6.2, are to continue their scheduled study assessments (as per Table 5.1-2 and Table 5.1-3) and may still be eligible to receive treatment in the Continuation Period, starting at Week 25.

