4.3.4 Dose Modifications for Nivolumab and Ipilimumab

Subjects will be monitored continuously for AEs while on study. Treatment modifications (eg, dose omissions) will be based on specific laboratory and AE criteria.

In some cases, the natural history of AEs associated with immunotherapy can differ and be more severe than AEs caused by other therapeutic classes. Early recognition and management may mitigate severe toxicity. The following Recommended Management Algorithms for nivolumab were developed to assist investigators and can be found in the BMS-936558 (nivolumab) Investigator Brochure:

- Suspected Pulmonary Toxicity
- Diarrhea and Colitis
- Suspected Hepatotoxicity (including asymptomatic LFT elevations)
- Suspected Endocrinopathy
- Suspected Nephrotoxicity

In addition, the ipilimumab Investigator Brochure⁵ includes Management Algorithms for the following adverse reactions:

- GI Toxicity
- Hepatotoxicity
- Skin Toxicity
- Endocrinopathy
- Neurological Toxicity
- Other immune-mediated adverse reactions, including ocular manifestations

It should be noted that beginning with the first dose of Induction Period 2, adverse events may be related to the drug given in Induction Period 2, the prior drug given in Induction Period 1, or to both drugs. Therefore, it is recommended that the Management Algorithms in both the BMS-936558 (nivolumuab) Investigator Brochure and the ipilimumab Investigator Brochure be consulted for assistance with managing adverse events after the beginning of Induction Period 2.

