6 ADVERSE EVENTS

An *Adverse Event (AE)* is defined as any new untoward medical occurrence or worsening of a preexisting medical condition in a clinical investigation subject administered an investigational (medicinal) product and that does not necessarily have a causal relationship with this treatment. An AE can therefore be any unfavorable and unintended sign (such as an abnormal laboratory finding), symptom, or disease temporally associated with the use of investigational product, whether or not considered related to the investigational product.

The causal relationship to study drug is determined by a physician and should be used to assess all adverse events (AE). The casual relationship can be one of the following:

- Related: There is a reasonable causal relationship between study drug administration and the AE.
- Not related: There is not a reasonable causal relationship between study drug administration and the AE.

The term "reasonable causal relationship" means there is evidence to suggest a causal relationship.

Adverse events can be spontaneously reported or elicited during open-ended questioning, examination, or evaluation of a subject. (In order to prevent reporting bias, subjects should not be questioned regarding the specific occurrence of one or more AEs.)

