8 STATISTICAL CONSIDERATIONS

8.1 Sample Size Determination

This trial is an estimation trial. Sample size in this study will be approximately 40 subjects per cohort and is not based on power considerations. Tables below provide the 95% confidence intervals computed from different observed rates. Those tables indicate what would be the reliability of the AE rate estimates for N=40 (Table 8.1-1) and N=35 (see Table 8.1-2) treated subjects. A threshold of 45% will be applied to the upper limit of the confidence interval as an informal guideline for high toxicity

Thirty-five subjects per cohort will be the minimum number of subjects receiving treatment in Induction Period 2. For that purpose, randomization will stay open until at least 40 subjects in each cohort have been treated with at least one dose of study treatment in Induction Period 1 and 35 subjects in each cohort have received at least one dose of study treatment in Induction Period 2. Assuming a drop-out rate during induction period 1 would be at most 12.5%, at least 35 subjects would be treated in induction period 2 if 40 subjects are to be randomized per cohort.

Table 8.1-1: Exact 95% CI width and upper bound for AE rates up to 40% when observed in 40 subjects

Nb Subj with Rel Gr3-5 A	Rate of Rel Gr3-5 AE	Exact 95% CI width	Upper limit Exact 95%CI
4	10%	21%	23.7%
8	20%	27%	35.6%
10	25%	29%	41.2%
11	27.5%	29%	43.9%
12	30%	30%	46.5%
13	32.5%	31%	49.1%
14	35%	31%	51.7%
16	40%	32%	57%

Table 8.1-2: Exact 95% CI width and upper bound for AE rates up to 40% when observed in 35 subjects.

Nb Subj with Rel Gr3-5 AE	Rate of Rel Gr3-5 AE	Exact 95% CI Width	Upper Limit Exact 95%CI
4	11.4%	23.5%	26.7%
7	20%	28.5%	36.9%
9	25.7%	30.8%	43.3%
10	28.6%	31.7%	46.3%
11	31.4%	32.4%	49.3%
14	40%	34%	57.9%

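### Does the repeat Period 2 safety table in Section 8.4.4 exclude events that the section's own onset rule has already left out?

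*Protocol*

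**What the plan says.** Section 8.4.4 describes safety separately for each period. For Induction Period 2 the rule is that "events considered will be those with an onset date during Induction Period 2", with subjects treated in that period as the denominator. The Period 1 rule mirrors it and closes at the switch: "AEs with an onset date after start of subsequent anti-cancer therapy, or start date of Induction Period 2 treatment will not be included". So an AE with a single onset date in Period 1 is counted in Period 1 only.

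The Period 2 paragraph ends with a sentence that the Period 1 paragraph lacks. It says that worst grades by organ class and preferred term during Period 2 will be reported, and it does not repeat the onset limit. The section then adds: "The same analysis will be performed excluding AEs persisting from Induction Period 1 that are downgraded in Induction Period 2", with the downgrading judged "compared to last grade observed in Induction Period 1".

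Three other places bear on this:

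- Section 3.1.2.2 expects AEs to be carried across Week 13. "Subjects with drug-related AEs after the last dose in Induction Period 1 who fail to meet retreatment criteria" still enter Period 2, with doses omitted until the criteria are met.
- Section 6 defines an AE as "any new untoward medical occurrence or worsening of a preexisting medical condition". An improvement is not listed.
- Section 4.3.4 notes that from the first Period 2 dose "adverse events may be related to the drug given in Induction Period 2, the prior drug given in Induction Period 1", or to both.

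**The concern.** A persisting AE by definition began before Period 2, so a rule based on onset in Period 2 leaves it out. Excluding some persisting AEs from that same set then has no effect. A planned analysis appears to be empty, and its table would repeat the main one line for line.

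There is a second worry. Excluding only the downgraded AEs suggests that AEs persisting at the same or a worse grade stay in, whereas the onset rule on its face drops them. Two programmers could follow the section faithfully and report different Period 2 rates. This trial compares two orders of giving the same drugs, and the Period 2 table is where a reader looks for toxicity after the switch. AEs carried over Week 13 are foreseen by design, so the question is not hypothetical.

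**Working it through.** The protocol gives no figure for this point, so there is nothing to reproduce. The check is to apply the stated rules under each plausible way of recording AEs.

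**Groups.** Let N be the subjects treated in Period 2 in one cohort. Let *a* be those with a treatment-related AE that is new in Period 2. Among the rest, let *b*, *c* and *d* be those whose only carried-over AE worsened, was downgraded, or stayed at the same grade. Subjects with mixed carried-over AEs are left aside, since they do not alter the argument. The rate of AEs that start or worsen in Period 2 is (a+b)/N.

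| Recording convention | Main table | Repeat table | Main minus repeat |
|---|---|---|---|
| One onset date per AE; worsening is not a new record | a/N | a/N | 0 |
| One onset date per AE; worsening is a new AE, as Section 6 allows | (a+b)/N | (a+b)/N | 0 |
| Every grade change is a separately dated record | (a+b+c)/N | (a+b)/N | c/N |
| AEs counted if present in Period 2, at the worst grade then | (a+b+c+d)/N | (a+b+d)/N | c/N |

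**What the rows show.**

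1. In the first two rows the repeat is redundant. This is the literal problem, and it is correct as far as it goes.
2. In the last two rows the repeat does real work: it removes Period 1 AEs that are improving.
3. The start-or-worsen rate appears in both tables in row 2 and in the repeat table in row 3. In row 4 the repeat exceeds it by d/N. Only in row 1 is it understated, by b/N, and row 1 requires setting aside the Section 6 definition, which counts a worsening as an AE.

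**Which row does the text favour?** The protocol states none of them. Comparing a Period 2 grade with the last grade seen in Period 1 needs grades dated within an event. That fits rows 3 and 4, though dated grades need not each have their own onset date. The closing sentence on worst grades during Period 2 would only repeat an earlier sentence unless it means grades present in Period 2, which fits row 4. The opening onset sentence favours rows 1 to 3. The section is therefore ambiguous, and the repeat is not necessarily empty.

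**Scale.** Section 8.1 says "Thirty-five subjects per cohort will be the minimum number of subjects receiving treatment in Induction Period 2". One subject is 1/35 = 2.9 points there, or 1/40 = 2.5 points at N=40. In Table 8.1-2, 9 of 35 is 25.7% with an exact 95% interval 30.8 points wide, so one subject is 2.86/30.8, about 9% of that width. These figures hold for any one-subject change. They do not measure this problem, because *b*, *c* and *d* cannot be derived from the protocol.

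**Reach.** The primary endpoint in Section 8.3.1 counts a subject once for any qualifying event over both induction periods. An AE carried across Week 13 already has its onset inside that window. The sensitivity analysis in Section 8.4.2 changes the set of subjects, not the event window. The 45% guideline in Section 8.1 is set out for the related Grade 3–5 AE rate, not for the by-period tables, and Section 8.4.4 attaches no threshold to them.

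**The case for a change.** The strongest case for a change is that both rules stand in the same section of the protocol. A statistical analysis plan that chose a convention would be repairing the text rather than adding detail to it. Nothing in the protocol says that a grade change opens a new record. Section 6 gives a worsening the status of an AE but not an improvement, so a downgraded AE gains no Period 2 onset from that definition. The study is open-label, and a convention chosen after data are seen could shift the reported rate after the switch. A clarifying sentence would be cheap and need no new data.

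Much of this stands. With one onset date per AE the two sentences do not fit, and no redaction or conversion fault explains it. One sentence on how a grade change is dated would make the section clearer.

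The step to a required change does not stand. How grade changes are recorded, and which date drives by-period counting, is usual content of an analysis plan, which is not shown here. Redefining Period 2 events as those that start or worsen would also be a change of analysis: it drops AEs persisting at the same grade, which the exclusion of downgraded AEs alone seems to keep. The worry about a late choice has little force, because both tables are planned and no decision hangs on either. A repeat table identical to the main one would be redundant, not misleading.

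**Conclusion.** No change to the plan is needed. Section 8.4.4 does not say whether Period 2 AEs are counted by onset, by dated grade change or by presence. On the strictest reading, its second Period 2 table duplicates the first. Analysts can fill this gap sensibly, and the section's own reference to the last Period 1 grade shows the direction.

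The effect is limited to descriptive tables by period. Main and repeat differ by zero under a single onset date and by c/N otherwise, with *c* unknown and possibly zero. These tables could not attribute an event to one drug in any case, as Section 4.3.4 acknowledges. The primary endpoint, its sensitivity analysis, the sample size tables and the 45% guideline are untouched.

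This rests on two assumptions: that the recording convention is fixed in the analysis plan or programming specifications before the tables are produced, and that a worsening is recorded as an AE in line with Section 6 or captured through dated grades. If neither form of recording were used, Period 2 would miss AEs that worsened after the switch. That would understate a descriptive rate by b/N and leave the trial's conclusions unchanged.

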8.4.7 Outcomes Research Analyses

Not Applicable.

8.4.8 Other Analyses

Not Applicable.

8.5 Interim Analyses

Not Applicable.

9 STUDY MANAGEMENT

9.1 Compliance

9.1.1 Compliance with the Protocol and Protocol Revisions

The study shall be conducted as described in this approved protocol. All revisions to the protocol must be discussed with, and be prepared by, BMS. The investigator should not implement any deviation or change to the protocol without prior review and documented approval/favorable opinion from the IRB/IEC of an amendment, except where necessary to eliminate an immediate hazard(s) to study subjects.

If a deviation or change to a protocol is implemented to eliminate an immediate hazard(s) prior to obtaining IRB/IEC approval/favorable opinion, as soon as possible the deviation or change will be submitted to:

- IRB/IEC for review and approval/favorable opinion
- BMS
- Regulatory Authority(ies), if required by local regulations
- Documentation of approval signed by the chairperson or designee of the IRB(s)/IEC(s) must be sent to BMS.

If an amendment substantially alters the study design or increases the potential risk to the subject: (1) the consent form must be revised and submitted to the IRB(s)/IEC(s) for review and approval/favorable opinion; (2) the revised form must be used to obtain consent from subjects currently enrolled in the study if they are affected by the amendment; and (3) the new form must be used to obtain consent from new subjects prior to enrollment.

If the revision is done via an administrative letter, investigators must inform their IRB(s)/IEC(s).

9.1.2 Monitoring

Representatives of BMS must be allowed to visit all study site locations periodically to assess the data quality and study integrity. On site they will review study records and directly compare them with source documents, discuss the conduct of the study with the investigator, and verify that the facilities remain acceptable.

In addition, the study may be evaluated by BMS internal auditors and government inspectors who must be allowed access to CRFs, source documents, other study files, and study facilities. BMS audit reports will be kept confidential.

The investigator must notify BMS promptly of any inspections scheduled by regulatory authorities, and promptly forward copies of inspection reports to BMS.

9.1.3 Investigational Site Training

Bristol-Myers Squibb will provide quality investigational staff training prior to study initiation. Training topics will include but are not limited to: GCP, AE reporting, study details and procedure, electronic CRFs, study documentation, informed consent, and enrollment of WOCBP.

9.2 Records

9.2.1 Records Retention

The investigator must retain all study records and source documents for the maximum period required by applicable regulations and guidelines, or institution procedures, or for the period specified by BMS, whichever is longer. The investigator must contact BMS prior to destroying any records associated with the study.

BMS will notify the investigator when the study records are no longer needed.

If the investigator withdraws from the study (eg, relocation, retirement), the records shall be transferred to a mutually agreed upon designee (eg, another investigator, IRB). Notice of such transfer will be given in writing to BMS.

9.2.2 Study Drug Records

It is the responsibility of the investigator to ensure that a current disposition record of investigational product (those supplied by BMS) is maintained at each study site where study drug and the following non-investigational product(s) are inventoried and dispensed. Records or logs must comply with applicable regulations and guidelines and should include:

- amount received and placed in storage area
- amount currently in storage area
- label identification number or batch number
- amount dispensed to and returned by each subject, including unique subject identifiers
- amount transferred to another area/site for dispensing or storage
- nonstudy disposition (eg, lost, wasted)
- amount destroyed at study site, if applicable

- amount returned to BMS
- retain samples for bioavailability/bioequivalence, if applicable
- dates and initials of person responsible for Investigational Product dispensing/accountability, as per the Delegation of Authority Form.

BMS will provide forms to facilitate inventory control if the investigational site does not have an established system that meets these requirements.

9.2.3 Case Report Forms

An investigator is required to prepare and maintain adequate and accurate case histories designed to record all observations and other data pertinent to the investigation on each individual treated or entered as a control in the investigation. Data that are derived from source documents and reported on the CRF must be consistent with the source documents or the discrepancies must be explained.

For sites using the BMS electronic data capture tool, electronic CRFs will be prepared for all data collection fields except for fields specific to SAEs and pregnancy, which will be reported on the paper or electronic SAE form and Pregnancy Surveillance form, respectively. Spaces may be left blank only in those circumstances permitted by study-specific CRF completion guidelines provided by BMS.

The confidentiality of records that could identify subjects must be protected, respecting the privacy and confidentiality rules in accordance with the applicable regulatory requirement(s).

The investigator will maintain a signature sheet to document signatures and initials of all persons authorized to make entries and/or corrections on CRFs.

The completed CRF, including any paper or electronic SAE/pregnancy CRFs, must be promptly reviewed, signed, and dated by the investigator or qualified physician who is a subinvestigator and who is delegated this task on the Delegation of Authority Form .For electronic CRFs, review and approval/signature is completed electronically through the BMS electronic data capture tool. The investigator must retain a copy of the CRFs including records of the changes and corrections.

Each individual electronically signing electronic CRFs must meet BMS training requirements and must only access the BMS electronic data capture tool using the unique user account provided by BMS. User accounts are not to be shared or reassigned to other individuals.

